36 (±2 weeks) weeks Androgen Deprivation Treatment (may start treatment before consenting to study) (may join study at any point of 36 weeks of treatment or at the end of treatment if PSA has normalized)

PSA Normalizes Start Radiation to all known sites of disease (if joining study after start of Androgen Deprivation Treatment, may start Radiation at the same time, if PSA normalized) (may join study after completion of 36 weeks of treatment and receive Radiation if Serum Testosterone remains at castrated levels)

End Androgen Deprivation Treatment when a total of 36 weeks of Treatment has been received

Follow until PSA Relapse Off Study Restart Androgen Deprivation Treatment Long term followup of patients: PSA, Local Control of stage IV disease, PFS, OS, site and number of new metastases, systemic treatments, long term toxicity.

1.0 OBJECTIVES

- To evaluate time to PSA relapse in patients with oligometastatic (≤ 5 lesions) hormone sensitive prostate cancer treated with 36 weeks of androgen deprivation and localized radiotherapy to all known tumor sites.
- To assess the Prostate-Specific Antigen (PSA) and objective response rate to treatment with 36 weeks of androgen deprivation and localized radiotherapy in patients with oligometastatic hormone-sensitive prostate cancer.
- 3) To assess the toxicity of 36 weeks of androgen deprivation and localized radiotherapy to oligometastases in patients with oligometastatic hormone-sensitive prostate cancer.
- 4) In appropriate situations evaluate the feasibility and toxicities of using helical tomotherapy image-guided IMRT to treat oligometastatic sites.
- 5) Long term follow-up of patients: PSA, Local Control of stage IV disease, PFS, OS, site and number of new metastases, systemic treatments, long term toxicity.

2.0 BACKGROUND AND HYPOTHESIS

2.1 Metastatic prostate cancer and cancer metastases:

Carcinoma of the prostate remains a significant health problem in the United States, with 230,000 new cases and 30,000 deaths estimated in 2004 (1). Despite progress in early detection thanks to the widespread use of serum Prostate Specific Antigen (PSA) about 15% of patients present with metastatic disease at diagnosis and 30% of patients suffer relapse to regional lymph nodes or distant organs despite local therapy.

Historically several hypotheses based on clinical evidence attempted to explain mechanisms of metastatic tumor cell spread. Halsted suggested that tumors spread in an orderly manner initially spreading to regional lymph nodes and then centrifugally to distant organs (2). In contrast the "systemic hypothesis" most clearly articulated by Fisher proposed two principal types of cancer: those that cannot metastasize and those that have metastasized widely before clinical detection (3). In an attempt to reconcile clinical and laboratory features in a unified hypothesis, the "spectrum" model has been proposed (4). This theory accepts that some tumors spread widely before clinical detectability while others never metastasize, but for the majority of cancers, metastatic capacity evolves during the clinical phase of tumor growth. During the evolutionary process there may be a stage, termed "oligometastases", when metastases are limited in number and location because metastatic capacity has not fully evolved (5).

With a few exceptions such as testis cancer and some hematologic malignancies, the treatment of metastatic cancer by hormonal or cytotoxic agents is rarely curative and in many instances ineffective. In this context an important question is whether in the natural history of metastatic spread there is a time when metastases are limited in number and/or in destination organs and therefore treatment with systemic agents augmented by regional treatments may be effective. Examples of this include resection of lung metastases from sarcoma, liver metastases from colorectal cancer and isolated resection of breast metastases (6,7,8). Despite their limitations hormone therapy and chemotherapy have been effective in eradicating subclinical deposits when used as an adjuvant to local therapy. But all too often

the tumor recurs in a few locations, the likely consequence of the large number of tumor cells at these sites or limited drug availability at the site. These remaining oligometastases then may serve as a nidus for further dissemination.

Since testosterone is the main growth and survival factor for prostate cancer most patients will respond initially to ablation of gonadal androgen production through surgical (bilateral orchiectomy) or medical (luteinizing hormone-releasing hormone [LHRH] agonist therapy) approaches (9). Combined androgen blockade is achieved by the addition of an androgen receptor blocker and confers small survival advantage over castration alone (10). Triple hormone therapy involves the use of LHRH agonist, antiandrogen agent and 5 alpha reductase inhibitor finasteride (Proscar®) that prevents conversion of testosterone to more potent dihydrotestosterone (DHT) (11). Unfortunately, eventually all patients will develop progressive disease despite continued androgen suppression, with a median time to progression of 14 to 30 months (12).

There are many mechanisms responsible for the development of resistance to androgen deprivation. They include amplification of androgen receptors, increased sensitivity of androgen receptors, mutations of androgen receptors that allow activation by non-androgenic ligands and activation of alternative survival pathways (13). There are several approaches that are proposed to circumvent or delay the development of androgen independence, but none of them have been proven clinically. Intermittent androgen deprivation has been shown to delay the development of hormone-refractory disease in preclinical models (14,15). Intermittent hormonal therapy usually consists of initial androgen deprivation for 6-12 months followed by an off - therapy interval until time of relapse (6-15 months). When PSA values meet threshold criteria (usually pre-treatment levels) treatment is re-started. Most of the initial responders (57-100 %) respond to re-treatment. This cyclic treatment continues until the development of hormone-refractory disease. While off-treatment, many patients experience improvement in their libidos, erections, hot flushes and energy (16). Unfortunately once resistance to hormone-refractory occurs, prognosis is dismal. This socalled "hormone- refractory prostate cancer" (HRPC) or "androgen - independent prostate cancer" is characterized by virulent biologic and clinical behavior with median survival of 18 months despite treatment with chemotherapy (17,18,19).

Metastatic prostate cancer is a heterogeneous disease and patients with \leq than 5 lesions have better survival than patients with > 5 metastatic lesions (20). It is more likely that patients with limited number of metastases will benefit from local therapy and the patients with \leq than 5 metastases will be the focus of this study.

We hypothesize that it is possible and safe to treat patients with prostate cancer oligometastases with androgen deprivation and localized radiotherapy and that aggressive treatment of oligometastases early in the course of disease when disease is still sensitive to hormone manipulation will improve treatment outcomes of patients with metastatic prostate cancer.

2.2 Helical tomotherapy

Rapid advances in computer and medical imaging technologies have resulted in the ability to deliver radiotherapy with greater precision and conformality. External beam radiotherapy

has traditionally relied on radiologic imaging to direct therapy to appropriate anatomic regions. The integration of CT imaging into radiation treatment planning, allows for a three dimensional view of each patient's tumor relative to dose-limiting adjacent normal organs, allowing for customized beam shaping, beam orientation and dose conformality. The use of 3D conformal radiotherapy allows for further escalation of dose, which has resulted in higher tumor control, while maintaining risks and side effects at acceptable levels.

Intensity modulated radiation therapy (IMRT) has opened a new era in radiation oncology. By delivering therapy from multiple directions using multiple segmented or modulated beamlets, one can now sculpt radiation doses to fit the unique shape of each patient's tumor, optimizing radiation delivery to complex volumes and regions of the body. Some compare IMRT to "painting" radiation with a finer brush, where more precise, conformal and sophisticated dose patterns are now possible. This has also resulted in a greater degree of conformal dose avoidance of adjacent normal organs. Dose escalation is now possible with IMRT, which was not possible with technology just a decade ago. For example, radiation doses for prostate cancer, which have been limited to approximately 7000 cGy with conventional technologies, are now >8000 cGy using IMRT. As a result, a significant improvement in tumor control and a reduction in bladder and rectal toxicities have been reported (21).

Helical tomotherapy (HT) represents the next major advance in external beam radiotherapy delivery systems. HT is an FDA approved radiation therapy delivery device, which is a marriage of spiral CT and IMRT technology. Specifically, a 6 MV linear accelerator is mounted on a CT ring gantry and rotates around the patient as the patient translates through the ring. The treatment fan beam is segmented using a 64-leaf collimator. Each leaf casts a 0.6 mm width shadow at 85 cm isocenter distance with the fan beam, which varies in width from 0.5 to 5 cm. The minimum voxel or beamlet size is therefore 5 x 6 mm. By rapid opening and closing of leaves as a function of gantry angle while the patient slides through the ring, helical tomotherapy provides unprecedented ability to sculpt radiation doses to complex shaped tumor regions while simultaneously avoiding dose to normal organs (22,23,24).

Evaluating HT treatment plans for prostate cancer demonstrated rapid drop-off of dose around the target (prostate gland) in all directions resulting in excellent sparing of rectum, bladder and femoral heads superior to prior IMRT techniques (25). It is predicted that for select patients with lung cancer, tumor doses as high as 16,000 cGy will be achievable while maintaining normal lung doses (and therefore risks) at comparable levels as with conventional delivery methods, which are limited to doses of 6,000 cGy to the tumor in most patients.

In addition, an array of detectors mounted on the same rotating gantry and positioned directly opposed to the beam source, gives the HT delivery system two unique capabilities not found on any other delivery systems. First, these detectors allow for the generation of megavoltage CT (MVCT) images using the 6 MV beam. Resolution and contrast of MVCT is more than adequate to easily distinguish tissue planes and organ boundaries. This allows the HT system to automatically align beam orientation to anatomic external landmarks and internal organs in 3 dimensions prior to each daily session, vastly improving the precision of

radiation delivery. Second, these same arrays can be used to monitor output of the beam as it exits through the patient, providing an additional level of dose verification. It is anticipated that future software and hardware modifications will allow for this type of "adaptive radiotherapy" to occur in real time, constantly modulating beam output to account for minute-by-minute variations in tumor and organ motion.

The advent of HT brings for the first time to the clinic the potential to deliver highly conforming dose distributions to large complex target shapes. For example, with HT shaping the dose to the entire pleural surface, while sparing lung parenchyma is now possible for patients with mesothelioma.

3.0 DRUG INFORMATION:

3.1 Zoladex® (Goserelin)

Description: Zoladex is an LHRH analog with substitutions for the L-amino acid Glycine in positions 6 and 10. These substitutions produce an analog with 50-100 times the potency and longer duration of action then naturally occurring peptide when assessed in acute animal tests.

Supply: Zoladex® is commercially available as either 3.6 mg (one month) or 10.8 mg (three month) pellet for subcutaneous injection.

Storage: The Zoladex® 3.6 mg depot is supplied with 16-gauge needle, and the Zoladex® 10.8 mg depot is supplied with a 14-gauge needle. The unit is sterile and comes in a sealed, light-and moisture-proof package. The pack should be stored at room temperature. Before being opened, each package must be inspected for damage in which case the syringe must not be used. Being sterile, the syringe should be removed from its package only by the physician/nurse immediately before use.

Administration: If requested by the patient, a local anesthetic, i.e., 0.2 to 0.5 ml of 1% lidocaine hydrochloride may be given intradermally. Zoladex® will be injected subcutaneously using an aseptic technique. Insert the needle to its full length, pull it back 1 cm, then inject. The manufacturer recommends inserting the needle into the subcutaneous fat then changing the direction of the needle so it parallels the abdominal wall before inserting the needle to its full length. This will create a little pocket for the Zoladex® plug so that it doses not extend when the needle is withdrawn. After checking to ensure that the depot has been discharged, the used syringe will be discarded in a safe manner. One can ensure that the depot has been discharged by ensuring that the tip of the plunger is visible within the tip of the needle. The tear off portion of the depot package label will be removed and affixed to the patient's permanent record.

Toxicity: During routine screening of Zoladex®, no significant pharmacological activity was apparent in the cardiovascular, respiratory, central nervous, renal, metabolic, coagulation or gastric systems. However, the following can occur: vasomotor, hot flashes, edema, gynecomastia, bone pain, thrombosis, decreased bone mineral density, lethargy,

dizziness, insomnia, anorexia, nausea, upper respiratory tract infection, rash, sweating, COPD, congestive heart failure, and GI disturbances. Please refer to the Package Insert for further information. Studies have shown that serum levels of testosterone can be reduced and maintained within the castrate range resulting in objective evidence of tumor regression. Other than the occasional transient worsening of cancer symptoms tumor flare due to an initial temporary rise in testosterone serum levels on initiating therapy, no significant toxicity apart from that attributed to castration has been reported. In general, allergic reactions have been extremely uncommon with Zoladex® therapy. There have been isolated reports of urethral obstruction, urticaria, or spinal cord compression.

3.2. Leupron® (leuprolide acetate implant)

Description: Leuprolide acetate is a synthetic nonapeptide analog of naturally occurring gonadotropin-releasing hormone (GnRH or LH-RH). The analog possesses greater potency than the natural hormone. Leuprolide acetate, an LH-RH agonist, acts as a potent inhibitor of gonadotropin secretion when given continuously and in therapeutic doses. Animal and human studies indicate that following an initial stimulation, chronic administration of leuprolide acetate results in suppression of ovarian and testicular steroidogenesis. This effect is reversible upon discontinuation of drug therapy. Administration of leuprolide acetate has resulted in inhibition of the growth of certain hormone dependent tumors (prostatic tumors in Noble and Dunning male rats and DMBA-induced mammary tumors in female rats) as well as atrophy of the reproductive organs. In humans, administration of leuprolide acetate results in an initial increase in circulating levels of luteinizing hormone (LH) and follicle stimulating hormone (FSH), leading to a transient increase in levels of the gonadal steroids (testosterone and dihydrotestosterone in males, and estrone and estradiol in premenopausal females. However, continuous administration of leuprolide acetate results in decreased levels of LH and FSH. In males, testosterone is reduced to castrate levels. In premenopausal females, estrogens are reduced to postmenopausal levels. These decreases occur within two to four weeks after initiation of treatment, and castrate levels of testosterone in prostatic cancer patients have been demonstrated for more than five years.

Supply: Leuprolide is commercially available as either 7.5 mg (one month), 22.5 mg (three month), or 30 mg (four month) depots for intramuscular injection. Each kit contains a vial of sterile lyophilized microspheres, which is leuprolide incorporated in a biodegradable polymer of polylactic acid. Any formulation may be used.

Storage: The vial of leuprolide and the ampule of diluent may be stored at room temperature. Product does not contain preservative; discard if not used immediately.

Administration: As with other drugs administered by injection, the injection site should be varied periodically.

Toxicity: In the majority of patients, testosterone levels increased above baseline during the first week, declining thereafter to baseline levels or below by the end of the second week of treatment. The most common side effect of Leuprolide is hypertension, depression, insomnia, headache, dizziness, nervousness, impotence, decreased libido, anorexia, nausea and vomiting, myalgia, neuromuscular disorders, dyspnea, anemia, skin reactions, asthenia,

and injection site reactions. Please refer to the Package Insert for further information. Potential exacerbations of signs and symptoms during the first few weeks of treatment is a concern in patients with vertebral metastases and/or urinary obstruction or hematuria which, if aggravated, may lead to neurological problems such as temporary weakness and/or paresthesia of the lower limbs or worsening of urinary symptoms.

3.3 Casodex® (bicalutamide)

Description: Casodex bicalutamide is a nonsteroidal antiandrogen, which has no androgenic or progestational properties. The chemical name is propanamide, N-[4-cyano-3(trifluoromethyl)phenyl]- 3- [(4fluorophenyl)sulphonyl]- 2- hydroxy- 2methyl, (+,-). Casodex is a racemic mixture with the antiandrogen activity residing exclusively in the (-) or (R) enantiomer. Casodex 50 mg has the status of an approved new drug. Casodex has a long half-life compatible with once-daily dosing. Casodex is well tolerated and has good response rates in phase 11 trials (Kennealey and Furr, 1991, Tyrrell 1994).

Supply: Casodex is commercially available as a 50 mg tablet.

Storage: Casodex should be stored in a dry place at room temperature between 69°-77°F.

Administration: Casodex is administered orally at a dose of one 50 mg tablet per day. Administration will be suspended only if there is an apparent or suspected reaction to the drug.

Toxicity: In animal experiments, birth defects (abnormal genitalia, hypospadias) were found in male offspring from female animals dosed with Casodex during pregnancy. Although offspring from male animals dosed with Casodex did not show any birth defects, patients enrolled in this trial are advised to neither cause pregnancy nor to donate sperm while receiving protocol therapy or during the first 3 months after cessation of therapy. The use of barrier contraceptives is advised.

The most frequent adverse events reported among subjects receiving bicalutamide therapy are breast tenderness, breast swelling, and hot flashes. Adverse events not directly related to the pharmacological properties of bicalutamide were infrequent. Nonpharmacological adverse events, reported in the trial using bicalutamide 50 mg as monotherapy include asthenia, pelvic pain, peripheral edema, pruritus, rash, constipation, impotence, dyspnea, nausea, hypertension, dizziness, paresthesia, insomnia, sweating, diarrhea, increased liver enzyme tests, nocturia, hematuria, UTI hyperglycemia, weight loss, anemia, and chest pain (Kaisary 1994). There has been no observed change in cardiac parameters during long-term administration of bicalutamide 50 mg daily.

When bicalutamide 50 mg was given in combination with an LHRH analogue, the LHRH analogue adverse event profile predominated with a high incidence of hot flashes (53%) and relatively low incidences of gynecomastia (4.7%) and breast pain (3.2%).

4.0 STAGING CRITERIA

STAGE	SUB- STAGE	DEFINITION
T1		Clinically unapparent tumor, not detected by DRE nor visible by imaging
	T1a	Incidental histologic finding; <5% of tissue resected during TURP
	T1b	Incidental histologic finding; >5% of tissue resected during TURP
	T1c	Tumor identified by needle biopsy due to elevated PSA
T2		Confined within the prostate (detectable by DRE)
	T2a	Tumor involves half of the lobe or less
	T2b	Tumor involves more than one half of one lobe but not both lobes
	T2c	Tumor involves both lobes
T3		Tumor extends through the prostate capsule but has not spread to other organs
	T3a	Extracapsular extension
	T3b	Tumor invades seminal vesicle(s)
T4		Tumor is fixed or invades adjacent structures other than seminal vesicles
	T4a	Tumor invades bladder neck and/or external sphincter and/or rectum
	T4b	Tumor invades levator muscles and/or is fixed to pelvic wall

STAGE	SUB- STAGE	DEFINITION
Node (N)		Regional lymph nodes
	N0	No lymph nodes metastasis
	N1	Metastasis in single lymph node <2 cm in greatest dimension
	N2	Metastasis in single lymph node >2cm but <5 cm in greatest dimension, or multiple lymph nodes, none >5 cm
	N3	Metastasis in lymph node >5 cm in greatest dimension

STAGE	SUB- STAGE	DEFINITION
Metastasis		Systemic spread
	M0	No distant metastasis
	M1a	Non-regional lymph node metastasis
	M1b	Bone metastasis 1) Axial skeleton only 2) Extending also to peripheral skeleton
	M1c	Metastasis at other sites

STAGE	SUB- STAGE	DEFINITION
Histopathologic		Differentiation
	GX	Grade cannot be assessed
	G1	Well differentiated (slight anaplasia)
	G2	Moderately differentiated (moderate anaplasia)
	G3	Poorly differentiated or undifferentiated (marked

STAGE GROUPING:

				Gleason
Ι	Tla	NO	M0	G1
П	Tla	NO	M0	G2, 3-4
	T1b	NO	M0	Any G
	T1c	NO	M0	Any G
	T1	N0	M0	Any G
	T2	N0	M0	Any G
III	T3	N0	M0	Any G
IV	T4	N0	M0	Any G
	Any T	N1or N2 or N3	M0	Any G
	Any T	Any N	M1a or M1b or M1c	Any G

5.0 ELIGIBILITY CRITERIA

5.1 Inclusion Criteria

- 5.1.1 Patients with histologically proven diagnosis of adenocarcinoma of the prostate stage N1, N2, N3, M1a, M1b, M1c with \leq 5 metastatic lesions. If the diagnosis of metastasis in the lymph node is based solely on imaging CT scan or MRI, the longitudinal diameter of the lymph node has to be \geq 2.0 cm. If the lymph node is positive on PET or Prostascint scan, the longitudinal diameter of the lymph node on CT scan or MRI has to be \geq 1.5 cm.
- 5.1.2 Patients who have measurable disease must have had X-rays, scans or physical examination used for tumor measurement completed within 28 days prior to registration. Patients must have non-measurable disease assessed within 42 days prior to registration.
- 5.1.3 Patients must have had documented PSA level of > 2 prior to onset of androgen deprivation.
- 5.1.4 Patients might have received up to 36 weeks of adjuvant androgen deprivation therapy and up to 36 weeks of androgen deprivation therapy for metastatic disease prior to enrollment to this study. Patients may be on androgen deprivation for metastatic disease at the time of enrollment to the protocol. Adjuvant therapy must have been completed at least 2 years before

androgen deprivation for metastatic disease and patients must remain hormone sensitive.

- 5.1.5 Prior radiation therapy for metastatic disease is not allowed.
- 5.1.6 Prior chemotherapy for metastatic disease is not allowed. Prior neoadjuvant and adjuvant chemotherapy is allowed. Patients must have recovered from all acute side-effects related to previous systemic therapy.
- 5.1.7 Patients are allowed to receive one prior systemic non-chemotherapeutic treatment (i.e. immunotherapy, receptor tyrosine kinase inhibitor, antiangiogenic agent, differentiating agent) for recurrent or metastatic disease. Patients must have recovered from all acute side-effects related to previous systemic therapy.
- 5.1.8 Use of bisphosphonates is allowed at the discretion of treating physician
- 5.1.9 Patients must be at least 18 years of age.
- 5.1.10 Patient must be capable of understanding the nature of the trial and must give written informed consent.
- 5.1.11 Patients must have a WHO Performance status of 0, 1, or 2.
- 5.2 Exclusion Criteria
 - 5.2.1 Patients with unstable or severe intercurrent medical conditions or active, uncontrolled infection.
 - 5.2.2 Patients with history of orchiectomy.
 - 5.2.3 Patients undergoing therapy with other investigational agents. Patients must have recovered from all acute effects of previously administered investigational agents and sufficient time must have elapsed since last administration to ensure the drug interactions not occur during this study.
 - 5.2.4 Patients with a history of brain metastases or who currently have treated or untreated brain metastases.
 - 5.2.5 Patients who have demonstrated refractoriness to hormone therapy with LHRH agonist. Refractoriness is defined as occurrence of one of the following while on therapy with LHRH agonist: Increase in PSA by 25% over baseline (to at least > 2 ng/ml) on two consecutive PSA measurements, 20% increase in the sum of longest diameters of target measurable lesions over smallest sum observed (over baseline if no decrease during therapy) using the same techniques as baseline, clear worsening of any non-measurable disease, reappearance of any lesion that had disappeared, appearance of any new lesion.

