6.0 TREATMENT PLAN

Treatment will be given according to the Schema described in section 6.1. A treatment may be stopped for up to 4 weeks to allow for recovery from toxicities. Patients unable to safely resume treatment at that point will be taken off study. 12 weeks constitutes one cycle of hormone therapy.

6.1 Treatment schedule:

- 6.1.1 Patients will begin radiation therapy only after they have demonstrated evidence of PSA normalization after initiation of androgen deprivation therapy (stable or declining PSA level of \leq 4 (or stable or declining PSA \leq pre-treatment level whichever is smaller) on two consecutive measurements. Patients who do not meet these criteria will be taken off protocol.
- 6.1.2 Patients will be divided into two strata:

Stratum 1:

a) Patients who are not on androgen deprivation therapy at the time of enrollment to the protocol will begin androgen deprivation and start radiation therapy after PSA normalization (see section 6.1.1)

b) Patients who are already treated with androgen deprivation therapy at the time of enrollment to the protocol (see 5.1.4) will continue androgen deprivation therapy and begin radiation after meeting criteria for PSA normalization (see section 6.1.1). Radiation therapy will be finished before 36 weeks (± 2 weeks) of hormone therapy is completed.

Stratum 2:

Patients who are enrolled on the protocol towards the end (or after completion) of 36 weeks (\pm 2 weeks) of androgen deprivation so radiation treatment cannot be finished before the completion of 36 weeks of androgen deprivation therapy can still initiate and/or complete radiation therapy as long as their serum testosterone level remains at the castrated levels (<50 ng/dL) and they meet the criteria for PSA normalization (section 6.1.1). Patients will not receive more than 36 weeks of androgen deprivation therapy.

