9.0 CRITERIA FOR EVALUATION AND ENDPOINT DEFINITIONS

Patients who complete radiation therapy and 1 cycle (12 weeks) of androgen deprivation treatment on protocol will be included in analysis of tumor response and time to PSA relapse

- 9.1 Disease Status
 - 9.1.1 Measurable disease: Lesions that can be accurately measured in at least one dimension by 1) medical photograph (skin or oral lesion), palpation, plain X-ray, CT, MRI, or other conventional technique with longest diameter 2 cm or greater in the axial plane (bone lesions not included), or 2) spiral CT with longest_diameter 1 cm or greater. Ultrasound is only suitable for superficial disease (superficial palpable nodules, subcutaneous lesions, thyroid lesions). Conventional CT and MRI should be performed with cuts of 10 mm or less in slice thickness contiguously. Spiral CT should be performed using a 5 mm contiguous reconstruction algorithm.
 - 9.1.2 Non-measurable disease: Lesions too small to be considered measurable, masses with margins not clearly defined, bone disease, pleural or pericardial disease, leptomeningeal disease, pneumonitis, lymphangitis.
- 9.2 Objective Status

(To be recorded at each evaluation.) All measurable lesions (patients eligible for this protocol will have no more than 5 metastases) should be identified at baseline. Measurements must be provided for all measurable lesions, while presence or absence must be noted for non-measurable disease. Unless progression is observed, objective status can only be determined when all measurable and non-measurable sites and lesions are assessed.

- 9.2.1 Partial response in non-measurable disease (PRNM). Decrease in PSA level of > 50% compared to baseline pre-treatment level. No progression of non-measurable disease. No new lesions.
- 9.2.2 Partial response (PR): Applies only to patients with at least one measurable lesion. Greater than or equal to 30% decrease under baseline in the sum of longest diameters of all target measurable lesions. No progression of non-measurable disease. No new lesions. All measurable and non-measurable lesions and sites must be assessed using the same techniques as baseline.

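### For patients already on androgen deprivation at entry, partial response in measurable disease is counted from a scan taken partway through treatment, so a pooled rate does not estimate response to the full regimen

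*Combined protocol and SAP*

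**What the plan says.** The second objective in Section 1.0 covers PSA response and the "objective response rate to treatment with 36 weeks of androgen deprivation and localized radiotherapy".

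For measurable disease, Section 5.1.2 requires imaging or examination "used for tumor measurement completed within 28 days prior to registration". For the rest it says: "Patients must have non-measurable disease assessed within 42 days prior to registration". The Section 8.0 calendar places both tumor assessments in its pre-enrollment column, with windows counted from day 1 of cycle 1. Nothing asks for imaging from before ADT.

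Section 5.1.4 allows "up to 36 weeks of androgen deprivation therapy for metastatic disease prior to enrollment to this study". Section 6.1.2 then defines three entry groups:

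- Stratum 1a: not on ADT at enrollment.
- Stratum 1b: "Patients who are already treated with androgen deprivation therapy at the time of enrollment to the protocol".
- Stratum 2: patients "enrolled on the protocol towards the end (or after completion) of 36 weeks" of ADT.

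Partial response in Section 9.2.2 is "Greater than or equal to 30% decrease under baseline in the sum of longest diameters of all target measurable lesions". Baseline is not given a date relative to ADT. The calendar reassesses tumors at the end of ADT or radiotherapy, whichever is later, and at PSA relapse.

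Three passages bear on who is counted. Section 9.0 restricts the tumor-response analysis to patients who complete radiotherapy and 12 weeks of ADT on protocol. Section 10 has the initial analysis take in everyone, with strata exploratory. Section 10.1 reports response for every eligible registered patient.

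**The concern.** The objective is a property of the whole regimen, but the only tumor measurement that every patient must have is tied to registration. For a Stratum 1a patient that scan precedes all ADT for metastatic disease, apart from any adjuvant course allowed by Section 5.1.4. For a Stratum 1b patient it falls partway through ADT. Lesion shrinkage before registration is then built into the starting size, and only what follows can count toward the 30% threshold.

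A single partial-response rate across both groups mixes response to the full regimen with response to the remainder of it. The result depends on how many patients happened to start ADT before enrolling. The planned exploratory split does not help, because Stratum 1 contains both 1a and 1b. A reader who compares the published rate with other series could not tell what it measures.

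**Working it through.** **The plan's own figure.** Objective response has no target rate, test or sample size. The only power figure is 83% for time to PSA relapse (Section 10: 28 patients, one-sided 0.05, medians 9 and 16 months, accrual a = 24 months, follow-up f = 12 months). With λ = ln 2 / median and uniform accrual,

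P(event) = 1 − [exp(−λf) − exp(−λ(a + f))] / (λa).

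Expected events are 22.9 under the null and 17.6 under the alternative. Power = Φ{[ln(16/9) − 1.645/√22.9] × √17.6} = 83.5%, which reproduces the stated figure. No tumor measurement enters this calculation.

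**How much prior ADT a counted patient can have.** Total ADT is 36 weeks (±2) and Section 9.0 requires 12 of them on protocol. The most that can precede registration is 36 − 12 = 24 weeks, or 38 − 12 = 26 with the window. A Stratum 1b patient at that limit is measured over the last 12 weeks of ADT plus radiotherapy. A Stratum 2 patient who enrolled after finishing ADT has 0 weeks on protocol and is not evaluable under Section 9.0. Such patients enter only if the wording of Sections 10 and 10.1 governs.

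**What the 30% rule then demands.** Let s be the proportional shrinkage in the sum of diameters before the registration scan. Partial response requires a final size of at most 0.7 × (1 − s) of the pre-ADT size, so

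- total shrinkage needed = 1 − 0.7(1 − s);
- a true total shrinkage of 45% reads as 1 − 0.55/(1 − s).

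| Shrinkage before registration (assumed) | Total shrinkage needed | True 45% reads as |
|---|---|---|
| 0% | 30% | 45% |
| 10% | 37% | 39% |
| 20% | 44% | 31% |
| 30% | 51% | 21% |
| 40% | 58% | 8% |

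At s = 30%, for example, 1 − 0.7 × 0.7 = 51% and 1 − 0.55/0.70 = 21%. The same patient qualifies as a partial response at s = 20% and fails at s = 30%.

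**Effect on a pooled rate, for illustration only.** The documents give neither response rates nor the patient mix. Let R be the rate from a pre-ADT scan, r the rate from an on-ADT scan, and w the share already treated. The pooled rate is (1 − w)R + wr.

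| Assumed R, r | w = 25% | w = 50% | w = 75% |
|---|---|---|---|
| 70%, 20% | 57.5% | 45% | 32.5% |
| 60%, 40% | 55% | 50% | 45% |

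The spread across these mixes is 25 points in the first row and 10 in the second. The size therefore depends on the assumed rates as much as on the mix.

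**The case against.** Several points on the other side are sound, and they limit the finding.

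- **Not all objective response is affected.** A reader might infer that the whole response rate rests on registration scans. It does not. Response in non-measurable disease (Section 9.2.1) compares PSA with the pre-treatment level, and Section 5.1.3 already requires a documented pre-ADT PSA. Complete response (Section 9.2.3) uses disappearance of disease and absolute PSA cut-offs. Section 9.1.2 counts bone disease as non-measurable, and Section 6.1.2 expects mostly bone or lymph node sites, so the affected subset is some unknown part of 28 patients.
- **Thirty-six weeks of prior ADT is not the evaluable case.** Section 5.1.4 taken alone invites that reading. Section 9.0 caps it at about 24 weeks, and Stratum 1b cannot reach 36 because its radiotherapy must finish before ADT ends.
- **Baseline is undefined rather than set wrongly.** Section 5.1.2 is an eligibility window. The calendar counts from day 1 of cycle 1, and Section 6.0 defines a cycle as 12 weeks of hormone therapy, so a reader could place baseline at the start of ADT. Section 5.2.5 also uses the term for LHRH treatment that may precede enrollment. But no scan from before ADT is required, so for pre-treated patients the registration scan is the only one sure to exist.
- **The endpoint carries little weight.** Section 10 does not list objective response among its secondary endpoints, and the activity judgement rests on median time to PSA relapse. That lowers the stakes, but the rate remains a stated objective and will be reported.

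What stands is the mismatch for partial response in measurable disease. None of these points removes it for Stratum 1b.

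**Conclusion.** The concern holds in a limited form. Partial response under Section 9.2.2, counted from the registration scan, leaves out shrinkage on earlier ADT in Stratum 1b patients, who may have had up to about 24 weeks of it. It also does so in Stratum 2 if Sections 10 and 10.1 override Section 9.0. Pooled with Stratum 1a, the rate does not estimate response to 36 weeks of ADT plus radiotherapy, and the Stratum 1/2 split does not repair this.

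The conclusion rests on taking the registration scan as baseline. A downward bias is a reasonable expectation but not a documented fact: it requires that lesions shrink on prior ADT, and the documents give no shrinkage data. On that assumption, 30% prior shrinkage raises the total needed from 30% to 51%. The pooled-rate figures are illustrations and should not be cited as estimates.

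It would be wrong to infer that the trial's main conclusion is at risk. The primary endpoint and its 83% power do not depend on tumor measurements.

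**What to change.** In Sections 9.0 and 10:

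1. State that the tumor-response baseline is the registration scan.
2. Report measurable-disease response separately by ADT exposure at registration: ADT for metastatic disease not yet started, versus already on or past it. Do not rely on Stratum 1 versus 2. Use only the first group to address the second objective, and label the other *response after registration*.
3. Reconcile Section 9.0 with Sections 10 and 10.1 on who is in the response analysis.

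The PSA-based definition in Section 9.2.1 needs at most a cross-reference to the pre-ADT value in Section 5.1.3.

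This is a change of wording and tabulation. It uses measurements and treatment histories that the plan already calls for, and it needs no new scans. The cost is smaller groups and wider intervals around each rate in a trial of 28 patients.
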